**Table 4: Criteria for Clinically Notable Vital Sign Abnormalities for Age  $\geq 12$  to  $< 16$  Years**

Parameter	High Threshold	Low Threshold
Systolic blood pressure	$> 131$ mmHg	$< 110$ mmHg
Diastolic blood pressure	$> 83$ mmHg	$< 64$ mmHg
Pulse	$> 100$ bpm	$< 60$ bpm
Temperature	$> 38.0^{\circ}\text{C}$	$< 35.5^{\circ}\text{C}$
Respiratory rate	$> 20$ breaths/min	$< 8$ breaths/min

**Table 5: Criteria for Clinically Notable Vital Sign Abnormalities for Age  $\geq 16$  to  $< 18$  Years**

Parameter	High Threshold	Low Threshold
Systolic blood pressure	$> 120$ mmHg	$< 90$ mmHg
Diastolic blood pressure	$> 85$ mmHg	$< 50$ mmHg
Pulse	$> 100$ bpm	$< 45$ bpm
Temperature	$> 38.0^{\circ}\text{C}$	$< 35.5^{\circ}\text{C}$
Respiratory rate	$> 20$ breaths/min	$< 8$ breaths/min

## **10. INTERIM ANALYSES**

No formal interim analysis is planned for this study.

## **11. CHANGES AND MODIFICATIONS TO THE ANALYSIS PLAN**

All versions of the SAP are listed in [Table 6](#).

**Table 6: Statistical Analysis Plan Versions**

SAP Version	Date
Original	10 MAY 2024

### **11.1. Changes to Protocol-Defined Analyses**

Not applicable.

### **11.2. Changes to the Statistical Analysis Plan**

Not applicable.

## APPENDIX A. PLANNED TABLES, FIGURES, AND LISTINGS

This appendix provides a list of the planned tables, figures, and listings for the Clinical Study Report. Standard tables will follow the conventions in the Standard Safety Tables v1.6.

The lists of tables, figures, and listings are to be used as guidelines. Modifications of the lists that do not otherwise affect the nature of the analysis will not warrant an amendment to the SAP.

### Tables

Table No.	Title	Population
Baseline and Demographics Characteristics		
1.1 Disposition		
1.1.1	Analysis Populations	FAS
1.1.2.1	Summary of Participant Disposition in the CT Period	FAS
1.1.2.2	Summary of Participant Disposition in the LTS Period	LTS-EV
1.1.3	Summary of Number of Participants Enrolled by Country and Site	FAS
1.1.4.1	Summary of Protocol Deviations for the CT Period	FAS
1.1.4.2	Summary of Protocol Deviations for the LTS Period	LTS-EV
1.2 Demography and Baseline Characteristics		
1.2	Summary of Demographics and Baseline Characteristics	FAS
1.3 Baseline Disease Characteristics		
1.3	Summary of Baseline Disease Characteristics	FAS
1.4 Prior Medication and Concomitant Medication		
1.4.1	Summary of Prior Medications	FAS
1.4.2	Summary of Prior Medications for Atopic Dermatitis	FAS
1.4.3.1	Summary of Concomitant Medications in the CT Period	FAS
1.4.3.2	Summary of Concomitant Medications in the LTS Period	LTS-EV
1.5+ Others		
1.5	Summary of General Medical History	FAS
Efficacy		
2.1 IGA		
2.1.1.1	Summary of Participants Achieving IGA-TS by Visit	FAS
2.1.1.2	Summary of Participants in Each Category of IGA Score by Visit	FAS
2.1.1.3	Summary of Participants Achieving an IGA score of 0 or 1 by Visit	FAS
2.1.1.4	Summary of Participants Achieving a Facial IGA score of 0 or 1 by Visit	FAS
2.2 EASI		
2.2.1	Summary of Participants Achieving EASI75 by Visit During the Treatment Period	FAS
2.2.2	Summary of EASI Score by Visit During the Treatment Period	FAS
2.3 Itch NRS Score		
2.3.1	Summary of Participants Achieving $\geq$ 4-Point Improvement in Itch NRS Score by Visit During the Treatment Period	FAS with baseline Itch NRS score $\geq$ 4
2.3.2	Summary of By-Visit Itch NRS Score	FAS
2.3.3	Summary of Participant Achieving $\geq$ 4-Point Improvement in Daily Itch NRS Score	FAS with baseline Itch NRS score $\geq$ 4
2.3.4	Summary of Daily Itch NRS Score	FAS

Table No.	Title	Population
2.4 BSA		
2.4.1	Summary and Analysis of Total %BSA Affected by AD	FAS
Safety		
3.1 Exposure		
3.1.1.1	Summary of Exposure in the CT Period	FAS
3.1.1.2	Summary of Exposure in the LTS Period	LTS-EV
3.1.1.3	Summary of Exposure from Baseline to Week 52	FAS
3.1.2	Summary of Study Drug Compliance in the CT Period	FAS
3.1.3	Summary of Study Drug Compliance in the LTS Period	LTS-EV
3.2 Adverse Events		
3.2.1.1.1	Overall Summary of Treatment-Emergent Adverse Events in the CT Period	FAS
3.2.1.1.2	Overall Summary of Treatment-Emergent Adverse Events in the CT Period by Sex	FAS
3.2.1.1.3	Overall Summary of Treatment-Emergent Adverse Events in the CT Period by Race	FAS
3.2.1.1.4	Overall Summary of Treatment-Emergent Adverse Events in the CT Period by Ethnicity	FAS
3.2.1.2.1	Overall Summary of Treatment-Emergent Adverse Events in the LTS Period	LTS-EV
3.2.1.2.2	Overall Summary of Treatment-Emergent Adverse Events in the LTS Period by Sex	LTS-EV
3.2.1.2.3	Overall Summary of Treatment-Emergent Adverse Events in the LTS Period by Race	LTS-EV
3.2.1.2.4	Overall Summary of Treatment-Emergent Adverse Events in the LTS Period by Ethnicity	LTS-EV
3.2.1.3.1	Overall Summary of Treatment-Emergent Adverse Events From Baseline to Week 52	FAS
3.2.1.3.2	Overall Summary of Treatment-Emergent Adverse Events From Baseline to Week 52 by Sex	FAS
3.2.1.3.3	Overall Summary of Treatment-Emergent Adverse Events From Baseline to Week 52 by Race	FAS
3.2.1.3.4	Overall Summary of Treatment-Emergent Adverse Events From Baseline to Week 52 by Ethnicity	FAS
3.2.2.1	Summary of Treatment-Emergent Adverse Events by MedDRA System Organ Class and Preferred Term in the CT Period	FAS
3.2.2.2	Summary of Treatment-Emergent Adverse Events by MedDRA System Organ Class and Preferred Term in the LTS Period	LTS-EV
3.2.2.3	Summary of Treatment-Emergent Adverse Events by MedDRA System Organ Class and Preferred Term From Baseline to Week 52	FAS
3.2.3.1.1	Summary of Treatment-Emergent Adverse Events by MedDRA Preferred Term in Decreasing Order of Frequency in the CT Period	FAS
3.2.3.1.2	Summary of Treatment-Emergent Adverse Events by MedDRA Preferred Term in Decreasing Order of Frequency in the CT Period by Sex	FAS
3.2.3.1.3	Summary of Treatment-Emergent Adverse Events by MedDRA Preferred Term in Decreasing Order of Frequency in the CT Period by Race	FAS

Table No.	Title	Population
3.2.3.1.4	Summary of Treatment-Emergent Adverse Events by MedDRA Preferred Term in Decreasing Order of Frequency in the CT Period by Ethnicity	FAS
3.2.3.2.1	Summary of Treatment-Emergent Adverse Events by MedDRA Preferred Term in Decreasing Order of Frequency in the LTS Period	LTS-EV
3.2.3.2.2	Summary of Treatment-Emergent Adverse Events by MedDRA Preferred Term in Decreasing Order of Frequency in the LTS Period by Sex	LTS-EV
3.2.3.2.3	Summary of Treatment-Emergent Adverse Events by MedDRA Preferred Term in Decreasing Order of Frequency in the LTS Period by Race	LTS-EV
3.2.3.2.4	Summary of Treatment-Emergent Adverse Events by MedDRA Preferred Term in Decreasing Order of Frequency in the LTS Period by Ethnicity	LTS-EV
3.2.3.3.1	Summary of Treatment-Emergent Adverse Events by MedDRA Preferred Term in Decreasing Order of Frequency From Baseline to Week 52	FAS
3.2.3.3.2	Summary of Treatment-Emergent Adverse Events by MedDRA Preferred Term in Decreasing Order of Frequency From Baseline to Week 52 by Sex	FAS
3.2.3.3.3	Summary of Treatment-Emergent Adverse Events by MedDRA Preferred Term in Decreasing Order of Frequency From Baseline to Week 52 by Race	FAS
3.2.3.3.4	Summary of Treatment-Emergent Adverse Events by MedDRA Preferred Term in Decreasing Order of Frequency From Baseline to Week 52 by Ethnicity	FAS
3.2.3.4.1	Summary of Application Site Reactions by MedDRA Preferred Term in Decreasing Order of Frequency in the CT Period	FAS
3.2.3.4.2	Summary of Application Site Reactions by MedDRA Preferred Term in Decreasing Order of Frequency in the LTS Period	LTS-EV
3.2.3.4.3	Summary of Application Site Reactions by MedDRA Preferred Term in Decreasing Order of Frequency From Baseline to Week 52	FAS
3.2.4.1	Summary of Grade 3 or Higher Treatment-Emergent Adverse Events by MedDRA System Organ Class and Preferred Term in the CT Period	FAS
3.2.4.2	Summary of Grade 3 or Higher Treatment-Emergent Adverse Events by MedDRA System Organ Class and Preferred Term in the LTS Period	LTS-EV
3.2.4.3	Summary of Grade 3 or Higher Treatment-Emergent Adverse Events by MedDRA System Organ Class and Preferred Term from Baseline to Week 52	FAS
3.2.5.1	Summary of Grade 3 or Higher Treatment-Emergent Adverse Events by MedDRA Preferred Term in Decreasing Order of Frequency in the CT Period	FAS
3.2.5.2	Summary of Grade 3 or Higher Treatment-Emergent Adverse Events by MedDRA Preferred Term in Decreasing Order of Frequency in the LTS Period	LTS-EV
3.2.5.3	Summary of Grade 3 or Higher Treatment-Emergent Adverse Events by MedDRA Preferred Term in Decreasing Order of Frequency From Baseline to Week 52	FAS

Table No.	Title	Population
3.2.6.1	Summary of Serious Treatment-Emergent Adverse Events by MedDRA System Organ Class and Preferred Term in the CT Period	FAS
3.2.6.2	Summary of Serious Treatment-Emergent Adverse Events by MedDRA System Organ Class and Preferred Term in the LTS Period	LTS-EV
3.2.6.3	Summary of Serious Treatment-Emergent Adverse Events by MedDRA System Organ Class and Preferred Term From Baseline to Week 52	FAS
3.2.7.1	Summary of Serious Treatment-Emergent Adverse Events by MedDRA Preferred Term in Decreasing Order of Frequency in the CT Period	FAS
3.2.7.2	Summary of Serious Treatment-Emergent Adverse Events by MedDRA Preferred Term in Decreasing Order of Frequency in the LTS Period	LTS-EV
3.2.7.3	Summary of Serious Treatment-Emergent Adverse Events by MedDRA Preferred Term in Decreasing Order of Frequency From Baseline to Week 52	FAS
3.2.8.1	Summary of Treatment-Related Treatment-Emergent Adverse Events by MedDRA System Organ Class and Preferred Term in the CT Period	FAS
3.2.8.2	Summary of Treatment-Related Treatment-Emergent Adverse Events by MedDRA System Organ Class and Preferred Term in the LTS Period	LTS-EV
3.2.8.3	Summary of Treatment-Related Treatment-Emergent Adverse Events by MedDRA System Organ Class and Preferred Term From Baseline to Week 52	FAS
3.2.9.1	Summary of Treatment-Related Treatment-Emergent Adverse Events by MedDRA Preferred Term in Decreasing Order of Frequency in the CT Period	FAS
3.2.9.2	Summary of Treatment-Related Treatment-Emergent Adverse Events by MedDRA Preferred Term in Decreasing Order of Frequency in the LTS Period	LTS-EV
3.2.9.3	Summary of Treatment-Related Treatment-Emergent Adverse Events by MedDRA Preferred Term in Decreasing Order of Frequency From Baseline to Week 52	FAS
3.2.10.1	Summary of Grade 3 or Higher Treatment-Related Treatment-Emergent Adverse Events by MedDRA System Organ Class and Preferred Term in the CT Period	FAS
3.2.10.2	Summary of Grade 3 or Higher Treatment-Related Treatment-Emergent Adverse Events by MedDRA System Organ Class and Preferred Term in the LTS Period	LTS-EV
3.2.10.3	Summary of Grade 3 or Higher Treatment-Related Treatment-Emergent Adverse Events by MedDRA System Organ Class and Preferred Term From Baseline to Week 52	FAS
3.2.11.1	Summary of Treatment-Related Serious Treatment-Emergent Adverse Events by MedDRA System Organ Class and Preferred Term in the CT Period	FAS
3.2.11.2	Summary of Treatment-Related Serious Treatment-Emergent Adverse Events by MedDRA System Organ Class and Preferred Term in the LTS Period	LTS-EV

Table No.	Title	Population
3.2.11.3	Summary of Treatment-Related Serious Treatment-Emergent Adverse Events by MedDRA System Organ Class and Preferred Term From Baseline to Week 52	FAS
3.2.12.1	Summary of Treatment-Emergent Adverse Events With a Fatal Outcome by MedDRA System Organ Class and Preferred Term in the CT Period	FAS
3.2.12.2	Summary of Treatment-Emergent Adverse Events With a Fatal Outcome by MedDRA System Organ Class and Preferred Term in the LTS Period	LTS-EV
3.2.12.3	Summary of Treatment-Emergent Adverse Events With a Fatal Outcome by MedDRA System Organ Class and Preferred Term From Baseline to Week 52	FAS
3.2.13.1	Summary of Treatment-Emergent Adverse Events Leading to Dose Interruption by MedDRA System Organ Class and Preferred Term in the CT Period	FAS
3.2.13.2	Summary of Treatment-Emergent Adverse Events Leading to Dose Interruption by MedDRA System Organ Class and Preferred Term in the LTS Period	LTS-EV
3.2.13.3	Summary of Treatment-Emergent Adverse Events Leading to Dose Interruption by MedDRA System Organ Class and Preferred Term From Baseline to Week 52	FAS
3.2.14.1	Summary of Treatment-Emergent Adverse Events Leading to Discontinuation of Ruxolitinib Cream by MedDRA System Organ Class and Preferred Term in the CT Period	FAS
3.2.14.2	Summary of Treatment-Emergent Adverse Events Leading to Discontinuation of Ruxolitinib Cream by MedDRA System Organ Class and Preferred Term in the LTS Period	LTS-EV
3.2.14.3	Summary of Treatment-Emergent Adverse Events Leading to Discontinuation of Ruxolitinib Cream by MedDRA System Organ Class and Preferred Term From Baseline to Week 52	FAS
3.2.15.1	Summary of Treatment-Emergent Adverse Events of Interest by MedDRA System Organ Class and Preferred Term in the CT Period	FAS
3.2.15.2	Summary of Treatment-Emergent Adverse Events of Interest by MedDRA System Organ Class and Preferred Term in the LTS Period	LTS-EV
3.2.15.3	Summary of Treatment-Emergent Adverse Events of Interest by MedDRA System Organ Class and Preferred Term From Baseline to Week 52	FAS
3.2.16.1	Summary of Treatment-Emergent Adverse Events of Interest by MedDRA Preferred Term in Decreasing Order of Frequency in the CT Period	FAS
3.2.16.2	Summary of Treatment-Emergent Adverse Events of Interest by MedDRA Preferred Term in Decreasing Order of Frequency in the LTS Period	LTS-EV
3.2.16.3	Summary of Treatment-Emergent Adverse Events of Interest by MedDRA Preferred Term in Decreasing Order of Frequency From Baseline to Week 52	FAS
3.3 Laboratory		
3.3.1	Summary of Laboratory Values - Hematology in the Treatment Period	FAS
3.3.2	Summary of Laboratory Values - Chemistry in the Treatment Period	FAS
3.3.3.1	Shift Summary of Hematology Laboratory Values in CTCAE Grade - to the Worst Abnormal Value in the CT Period	FAS

Table No.	Title	Population
3.3.3.2	Shift Summary of Hematology Laboratory Values in CTCAE Grade - to the Worst Abnormal Value in the LTS Period	LTS-EV
3.3.4.1	Shift Summary of Chemistry Laboratory Values in CTCAE Grade - to the Worst Abnormal Value in the CT Period	FAS
3.3.4.2	Shift Summary of Chemistry Laboratory Values in CTCAE Grade - to the Worst Abnormal Value in the LTS Period	LTS-EV
3.3.5.1	Shift Summary of Hematology Values - to the Worst Abnormal Value in the CT Period	FAS
3.3.5.2	Shift Summary of Hematology Values - to the Worst Abnormal Value in the LTS Period	LTS-EV
3.3.6.1	Shift Summary of Chemistry Values - to the Worst Abnormal Value in the CT Period	FAS
3.3.6.2	Shift Summary of Chemistry Values - to the Worst Abnormal Value in the LTS Period	LTS-EV
3.4 Vital Signs		
3.4.1	Summary of Systolic Blood Pressure in the Treatment Period	FAS
3.4.2	Summary of Diastolic Blood Pressure in the Treatment Period	FAS
3.4.3	Summary of Pulse in the Treatment Period	FAS
3.4.4	Summary of Respiratory Rate in the Treatment Period	FAS
3.4.5	Summary of Body Temperature in the Treatment Period	FAS
3.4.6	Summary of Height in the Treatment Period	FAS
3.4.7	Summary of Weight in the Treatment Period	FAS

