5.1. Inclusion Criteria

Participants are eligible to be included in the study only if all of the following criteria apply:

- 1. Adolescents aged \geq 12 years to \leq 18 years (at the screening visit).
- 2. A diagnosis of AD as defined by the Hanifin and Rajka (1980) criteria.
- 3. Duration of AD of at least 2 years.
- 4. Total IGA score of 2 to 3 at the screening and baseline visits.
- 5. Percent BSA (excluding the scalp) with AD involvement of 3% to 20% at the screening and baseline visits.
- 6. Atopic dermatitis not adequately controlled with other topical prescription therapies or when those therapies are not advisable. See Section 8.1.5.2 for further details.
- 7. Agree to discontinue all agents used to treat AD from screening through the final follow-up visit.
- 8. Willingness to avoid pregnancy or fathering children based on the criteria below.
 - a. Male participants with reproductive potential must agree to take appropriate precautions to avoid fathering children from screening through 90 days (a spermatogenesis cycle) after the last application of ruxolitinib cream and must refrain from donating sperm during this period. Permitted methods in preventing pregnancy (see Appendix A) should be communicated to the participants and their understanding confirmed.
 - b. Female participants who are WOCBP must have a negative serum pregnancy test at screening and a negative urine pregnancy test before the first application of ruxolitinib cream on Day 1 and must agree to take appropriate precautions to avoid pregnancy from screening through 30 days (1 menstrual cycle) after the last application of ruxolitinib cream and must refrain from donating oocytes during this period. Permitted methods in preventing pregnancy (see Appendix A) should be communicated to the participants and their understanding confirmed.
 - c. A female participant not considered to be of childbearing potential as defined in Appendix A is eligible.
- 9. Ability to comprehend and willingness to sign an ICF or written informed consent of the parent(s) or legal guardian(s) and written assent from the participant when possible.
 - *Note:* Participants who become legal adults during the study will be asked for their signed consent to continue the study, and in the event of lack thereof, will be discontinued from further participation.

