5.2. Exclusion Criteria

Participants are excluded from the study if any of the following criteria apply:

- 1. An unstable course of AD (spontaneously improving or rapidly deteriorating) as determined by the investigator in the 4 weeks prior to baseline.
- 2. Concurrent conditions and history of other diseases:
 - a. Immunocompromised (eg, lymphoma, acquired immunodeficiency syndrome, Wiskott-Aldrich syndrome).
 - b. Chronic or acute infection requiring treatment with systemic antibiotics, antivirals, antiparasitics, antiprotozoals, or antifungals within 2 weeks before baseline.
 - c. Active acute bacterial, fungal, or viral skin infection (eg, herpes simplex, herpes zoster, chickenpox) within 1 week before baseline.
 - d. Any other concomitant skin disorder (eg, generalized erythroderma such as Netherton syndrome), pigmentation, or extensive scarring that, in the opinion of the investigator, may interfere with the evaluation of AD lesions or compromise participant safety.
 - e. Presence of AD lesions only on the hands or feet without prior history of involvement of other classic areas of involvement such as the face or the flexural folds.
 - f. Other types of eczema.
 - g. Current or history of hepatitis B or C virus infection.
- 3. Any current and/or history of serious illness or medical, physical, or psychiatric condition(s) that, in the investigator's opinion, would interfere with full participation in the study, including application of study cream and attending required study visits; pose a significant risk to the participant; or interfere with interpretation of study data. For example:
 - a. Clinically significant or uncontrolled cardiovascular disease, including unstable angina, acute myocardial infarction or stroke within 6 months from Day 1 of study cream application, New York Heart Association Class III or IV congestive heart failure, and arrhythmia requiring therapy or uncontrolled hypertension (blood pressure > 150/90 mm Hg) unless approved by the medical monitor/sponsor.
 - b. Current and/or history of malignancy in the 5 years preceding the baseline visit, except for adequately treated, nonmetastatic nonmelanoma skin cancer.
 - c. Current and/or history of arterial or venous thrombosis, including DVT and PE.
 - d. Current and/or history of active tuberculosis or current and/or history of latent tuberculosis unless adequately treated.
- 4. Any of the following clinical laboratory test results at screening:

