8.2.3. Investigator's Global Assessment

Investigator's Global Assessment is an overall eczema severity rating on a 0 to 4 scale that will be assessed for the whole body (total IGA) and for the face only (facial IGA) during site visits as outlined in the SoA (see Table 3 [CT period] and Table 4 [LTS period]). The area "Face" is defined as including the area on the forehead to the original hairline, on the cheek to the jawline vertically to the jawline and laterally from the corner of the mouth to the tragus. The area "Face" will not include the surface area of the lips, scalp, ears, or neck but will include the nose and eyelids. The severity strata for the IGA are shown in Table 8.

Table 8: Investigator's Global Assessment

Grade	Severity	Status
0	Clear	No erythema or induration/papulation, no oozing/crusting; there may be minor residual discoloration
1	Almost clear	There may be trace faint pink erythema, with almost no induration/papulation, and no oozing/crusting
2	Mild	There may be faint pink erythema, with mild induration/papulation and no oozing/crusting
3	Moderate	There may be pink-red erythema with moderate induration/papulation and there may be some oozing/crusting
4	Severe	There may be deep or bright red erythema with severe induration/papulation and with oozing/crusting

Source: FDA 2012.

Participants must have a total IGA score of 2 or 3 at the screening and baseline visits to enroll in the study; there is no limitation for total or facial IGA score at Week 8 (baseline for the LTS period) to enter the LTS period.

During the LTS period, including Week 8 (baseline for the LTS period), total IGA will be evaluated by the investigator to determine whether the participant requires continuation of treatment or should (re)enter an observation/no treatment cycle. If the total IGA score is ≥ 1, the participant will start or continue active treatment with ruxolitinib cream 1.5% BID. If the total IGA score is 0 (clear), the participant will (re)enter an observation/no treatment cycle.

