### **5.3. Analysis Populations**

#### **5.3.1. Full Analysis Set**

The FAS will include all participants who applied ruxolitinib cream at least once.

The FAS will be used for the summary of demographics, baseline characteristics, participant disposition, analyses of all efficacy data, and safety for the CT period and for the whole study as well.

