## Figures

Figure No.	Title	Population
4.1 IGA		
4.1.1	Proportion of Participants Achieving an IGA Score of 0 or 1 by Visit	FAS
4.1.2	Proportion of Participants Achieving a facial IGA Score of 0 or 1 by Visit	FAS
4.2 EASI		
4.2.1	Proportion of Participants Achieving EASI75 by Visit	FAS
4.2.4.1	Mean and Standard Error Plot of EASI Score by Visit	FAS
4.2.4.2	Mean and Standard Error Plot of Change From Baseline in EASI Score by Visit	FAS
4.2.4.3	Mean and Standard Error Plot of Percent Change From Baseline in EASI Score by Visit	FAS
4.3 Itch NRS		
4.3.1	Proportion of Participants Achieving $\geq$ 4-Point Improvement in Itch NRS Score by Visit	FAS with baseline Itch NRS score $\geq$ 4
4.3.2.1	Mean and Standard Error Plot of Itch NRS Score by Visit	FAS
4.3.2.2	Mean and Standard Error Plot of Change From Baseline in Itch NRS Score by Visit	FAS
4.3.2.3	Mean and Standard Error Plot of Percent Change From Baseline in Itch NRS Score by Visit	FAS
4.3.3	Proportion of Participants Achieving $\geq$ 4-Point Improvement in Daily Itch NRS Score	FAS with baseline Itch NRS score $\geq$ 4

Figure No.	Title	Population
4.3.4.1	Mean and Standard Error Plot of Daily Itch NRS Score	FAS
4.3.4.2	Mean and Standard Error Plot of Change From Baseline in Daily Itch NRS Score	FAS
4.3.4.3	Mean and Standard Error Plot of Percent Change From Baseline in Daily Itch NRS Score	FAS
4.4 BSA		
4.4.1	Mean and Standard Error Plot of AD-Affected %BSA by Visit	FAS
4.4.2	Mean and Standard Error Plot of Change From Baseline in AD-Affected %BSA by Visit	FAS
4.4.3	Mean and Standard Error Plot of Percent Change From Baseline in AD-Affected %BSA by Visit	FAS
4.5 Laboratory Data		
4.5.1	Mean and Standard Error Plot of Selected Laboratory Hematology Values by Visit	FAS
4.5.2	Mean and Standard Error Plot of Change From Baseline in Selected Laboratory Hematology Values by Visit	FAS
4.5.3	Mean and Standard Error Plot of Percentage Change From Baseline in Selected Laboratory Hematology Values by Visit	FAS
4.6.1	Mean and Standard Error Plot of Selected Laboratory Chemistry Values by Visit	FAS
4.6.2	Mean and Standard Error Plot of Change From Baseline in Selected Laboratory Chemistry Values by Visit	FAS
4.6.3	Mean and Standard Error Plot of Percentage Change From Baseline in Selected Laboratory Chemistry Values by Visit	FAS

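### As labelled, the facial IGA 0/1 displays use the whole FAS, so participants whose face is clear or almost clear at baseline can count as responders from the start

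*SAP*

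**What the plan says.** SAP Appendix A lists Table 2.1.1.4, "Summary of Participants Achieving a Facial IGA score of 0 or 1 by Visit", and Figure 4.1.2, "Proportion of Participants Achieving a facial IGA Score of 0 or 1 by Visit". The population column reads FAS for both. SAP 5.3.1 defines that set without any condition on the face: "The FAS will include all participants who applied ruxolitinib cream at least once".

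Eligibility restricts total IGA and not facial IGA. Protocol 5.1 requires "Total IGA score of 2 to 3 at the screening and baseline visits", and Protocol 8.2.3 repeats it: "Participants must have a total IGA score of 2 or 3 at the screening and baseline visits to enroll in the study". Protocol 8.2.3 treats facial IGA as a separate score on the same 0 to 4 scale. The only eligibility text that mentions the face is an exclusion in Protocol 5.2, "Presence of AD lesions only on the hands or feet without prior history of involvement of other classic areas of involvement". It turns on past involvement and does not require current facial lesions.

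SAP 6.1.2 summarises baseline facial IGA without a range, whereas it lists baseline IGA as 2 or 3. For the 4-point itch response, Appendix A narrows the population to "FAS with baseline Itch NRS score" of at least 4.

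**The concern.** Facial IGA 0 or 1 is an absolute state and needs no improvement from baseline. A participant whose AD is confined to the limbs can enter with facial IGA 0, meets the criterion on Day 1, and keeps meeting it for as long as the face stays clear. The title speaks of achieving the score, so a reader will naturally take the percentage as facial response.

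Among the planned responder displays, only the facial ones can be met at baseline:

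- Total IGA 0/1: everyone enters at 2 or 3.
- IGA-TS: requires an improvement of at least 2 grades.
- EASI75: requires an improvement of at least 75%.
- Itch 4-point response: limited to those with a baseline score of at least 4.

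What is at stake is how one exploratory percentage is read. With a single arm, there is no comparison group in which the same baseline contribution would appear.

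**Working it through.** The documents give no facial IGA figure, so there is none to reproduce. The only design input used is the planned enrolment of about 100 (Protocol 10.1).

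**Assumed inputs (none is in the documents)**

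- f: share of the FAS with baseline facial IGA 0 or 1, taken as 20% to 60%.
- s: share of those participants who are at 0 or 1 at the visit, taken as 90% or 100%.
- r: share at 0 or 1 at the visit among those with baseline facial IGA of 2 or more, taken as 0% to 70%.

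**Formulas**

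- Displayed rate in the FAS = f × s + (1 − f) × r.
- Difference from r = f × s + (1 − f) × r − r = f × (s − r). This is upward when s exceeds r and downward when it does not.

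**Displayed rate with s = 100%**

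| f | r = 0% | r = 30% | r = 50% | r = 70% | n with baseline facial IGA ≥ 2, of 100 |
|---|---|---|---|---|---|
| 20% | 20% | 44% | 60% | 76% | 80 |
| 40% | 40% | 58% | 70% | 82% | 60 |
| 60% | 60% | 72% | 80% | 88% | 40 |

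With s = 90% and r = 50%, the display shows 0.2 × 0.9 + 0.8 × 0.5 = 58% at f = 20%, and 0.6 × 0.9 + 0.4 × 0.5 = 74% at f = 60%.

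**Two worked cases**

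- f = 30%, s = 90%, r = 70%: displayed 0.27 + 0.49 = 76%; shift 0.3 × (0.9 − 0.7) = 6 points.
- f = 60%, s = 100%, r = 50%: displayed 0.60 + 0.20 = 80%; shift 0.6 × (1.0 − 0.5) = 30 points.

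**Can a reader recover r from the other planned tables?** Only within bounds. Table 1.3 should give f. Suppose f = 40% and the display shows 70%. Then r = (0.70 − 0.4 × s) / 0.6. With s = 100%, r = 0.30 / 0.6 = 50%. With s = 90%, r = 0.34 / 0.6 = 57%. With no limit on s, r could be as high as 100% (at s = 25%). Appendix A lists a by-visit category table for IGA (2.1.1.2) but no table labelled as its facial counterpart. The exact rate would have to be rebuilt from the participant-level Listing 2.6.2.

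**Cost in precision.** At a rate of 50%, the approximate 95% half-width is 1.96 × √(0.25 / n): 9.8 points at n = 100, 11.0 at n = 80, 12.7 at n = 60 and 15.5 at n = 40.

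**The case against.** The strongest objection is that the governing text cannot be read. The SAP contents place 7.3.1 on page 14 and Section 8 on page 17, but in the public version the 7.3.1 heading is followed directly by Section 8. The exploratory rows of the objectives tables are not visible either. A baseline condition for the facial outcome could sit there. An FAS label also does not settle the denominator in this SAP: Section 9.3.2 uses the number of participants in the baseline category for the CTCAE shift percentages, while Tables 3.3.3.1 and 3.3.4.1 are labelled simply FAS. Appendix A describes its lists as guidelines. This stands, and it limits confidence. The restricted itch label in the same column points the other way but is not conclusive.

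Second, the itch parallel is inexact. Someone below 4 at baseline cannot improve by 4 points, so that restriction is forced, whereas anyone can hold, gain or lose facial IGA 0/1. The FAS proportion therefore has a fair descriptive reading as the share of the treated cohort with a clear or almost clear face. Protocol 6.1 also allows new areas to arise and be treated, so a face that is clear at baseline can become involved. This stands too, and it is why the participants removed by a filter should still be reported.

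Third, baseline facial IGA is summarised, so the mixture is not hidden. This holds in part: the baseline summary bounds the response rate but does not give it.

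A reader might infer that the plan overstates the effect on the face. The documents do not support that. The size and direction depend on three unknown quantities, a restriction may exist in text that cannot be seen, and the visible plan does not present this proportion as a treatment effect.

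**Conclusion.** The point holds on the visible text. Both displays are labelled FAS, no entry criterion requires facial disease, and the outcome can be met before treatment. If 7.3.1 does contain a baseline restriction, the point reduces to aligning the two labels with it.

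The shift is f × (s − r). The 6-point and 30-point examples show how far it can vary under assumed inputs and are not estimates for this trial. It is small if few participants start with a clear or almost clear face.

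A reader might also infer that the trial's main findings are at risk. They are not: SAP 7.3 makes all efficacy analyses exploratory and without p-values, and the primary and secondary endpoints are safety and PK. Confidence is moderate and importance low to moderate. The change is worth making because it is cheap and lets the percentage measure what its title says.

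**What to change.** - Set the population of Table 2.1.1.4 and Figure 4.1.2 to *FAS with baseline facial IGA score ≥ 2*. A cut at 1 or more would keep participants at grade 1, who already meet the outcome.
- State the n in that subset at each visit.
- Report separately those with baseline facial IGA 0 or 1: the number remaining at 0 or 1 and the number reaching 2 or more, so that new facial disease is not lost.
- If 7.3.1 already defines a restriction, make both labels match it.

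The cost is a filter on a baseline score that is already collected, two label changes and a few added rows. The denominator becomes smaller, with the wider intervals shown above, and the displayed rate is less favourable whenever s exceeds r.
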